Delivery team: The FPM senior management team consists of [name] (Project Director/FPM CEO) who will oversee the implementation and clinical quality assurance and [name] (FFT-G Programme Manager) who will be the main contact person for the project. [name] (FPM CEO/Business Director) will provide back-up support, implementation advice and monitoring feedback reports. FPM Data Analyst, [name], will be involved throughout the project, especially during the mobilisation period to ensure the development of efficient data systems (e.g. study consultation tracker, case management spreadsheets, joined research and provider tracker), which proved indispensable for the successful delivery of the pilot RCT.

Each Borough will have a designated FFT-G team consisting of one clinical supervisor/supervisor-in-training and two therapists with dedicated admin support. In this

first year the supervisor in training will act as the operational manager of the team and will provide case management oversight of therapist activities and promote adherence to the model whilst holding their own (reduced) caseload of two families. They will also be responsible for identifying eligible cases through data retrieval and review processes and in offering consultations to allocated workers. They will be trained in this process and supported by the Programme Manager.

In addition, we will include a floating/peripatetic FFT-G therapist who can work across all three Boroughs to (a) ensure sufficient coverage in cases of therapist illness/maternity leave/annual leave/turnover; (b) manage capacity in demand. This will need to be a therapist with some prior FFT experience. We consider that this post will provide assurance against workflow fluctuations and also as a mitigation against staff sickness and turnover.

In the second year, supervisors will then also be doing the weekly supervision of the clinical work with training of the supervisor provided by FFT-LLC as we move the second stage of the FFT licence.

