The size of the FFT teams was decided upon the capacity needed to work with 144 families over the randomisation period. To generate this capacity we considered 3 teams, each with 2 therapists and 1 supervisor. This will give a capacity of 14 cases over 5 months for each team. Each team will be able to recruit 3-4 new families over 15 months (cycles of 5/6 months to allow completion of cases) for the RCT. There will of course be some attrition which will create some flexibility, but we need to aim for full capacity on completion.

The 3 teams will each be supported by a part time business officer. We will allocate one day a week of input from the Data Analyst and ongoing oversight from the Programme Manager. Leadership will be provided by the full time Programme Manager and part time (three days a week) Programme Director for general oversight. The Programme Manager and Data Analyst will be the main contact points to liaise with the Greenwich research team and to ensure the collection of all necessary data from the teams. To this central FPM administration team, we also propose adding a Data and Referral Officer. The postholder will set up the initial meeting between the family and research team (and all other associated administrative tasks), but will remain blind to research data and will only have access to the FPM/University of Greenwich case tracker spreadsheet to ensure oversight of recruitment and throughput issues. They will have no role in the administration of research questionnaires or consent forms although may collect them in a sealed envelope.

Evaluation team:

The senior evaluation team will consist of some the same team that led the YEF funded pilot feasibility trial of FFT-G, namely, [name] (PI; University of Greenwich), and

Professor (Co-I) [name] (Co-I; Royal Holloway, University of London). In addition, [name] (Co-I; University of Greenwich) will also be a Co-I. The team will also consist of a research team consisting of one Research Fellow and up to three research assistants.

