		Attachment representation measured by YP report: AAQ (Bodfield et al., 2020)	

YP self-efficacy measured by YP report: NGSE (Chen et al., 2001)

CU traits measured by YP and parent report: CU Traits MAP (Hawes et al., 2020)

Temperamental irritability measured by YP report: ODD subtyping DSM items (Stringaris & Goodman, 2009)

YP School attendance and truancy measured by parent report; and YP report from ISRD4

Age; gender; ethnicity; SES; household composition; parent relationship to YP measured by parent and/or YP report

Service being seen; days from first caseworker contact to randomisation measured by administrative data

Sample size calculations overview

Sample size calculations are not determined on the basis of a priori MDES but rather results from the pilot RCT.

		Protocol	Randomisation
Pilot study Effect Size		g = 0.36 [-0.32,1.03]	
Pre-test/ post- test correlations	level 1 (participant)	0.523	
Alpha ⁶		0.05	
Power		0.8	
One-sided or two-sided?		One sided	

⁶ Please adjust as necessary for trials with multiple primary outcomes, 3-arm trials, etc., when a Bonferroni correction is used to account for family-wise errors.

9

			Protocol	Randomisation
Number of participants		Intervention	144	
	of	Control	144	
	Total	288		

Sample size estimates for a full efficacy RCT were calculated using clincalc.com and checked against G^* Power calculations. Estimates used 80% power and p = 0.05 with an enrolment ratio of 1. Power calculations used one-sided tests because there is no recorded case of FFT having iatrogenic effects.

The primary outcome in the efficacy study is *Offending*: Self-reported delinquency (SRD) - International Self-Report Delinquency Study 4 survey offending scale (ISRD4; Marshall et al., 2022). This was not the primary outcome in the pilot study. Whilst a number of trials of FFT have been conducted with offending as a primary outcome, and a previous trial of FFT-G did include delinquency as a primary outcome, it recruited court mandated youth who were offending. The focus of the pilot was instead YP at risk of criminal exploitation recruited from social care.

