Therefore, the anticipated primary outcome in the pilot study was CCE as recorded on agency systems. During the pilot study, it became clear that this was not recorded reliably and so two co-primary outcomes collected directly from participants were used instead: PCG reported family functioning (total scale score) and YP reported conduct problems (CP; subscore of the SDQ). As a result, power calculations for this efficacy trial did not make use of SRD data from the pilot study. Based on the effect size for PCG-reported Family Functioning outcome in the pilot study (g = 0.36 (-0.32,1.03)), clincalc.com returned 238 participants, increased to 288 to account for up to 10% loss to follow-up at each assessment time point. Based on the effect size for YP-reported CP (g = 1.15 (0.13,1.52)), clincalc.com returned 42 participants, increased to 51 to account for 10% loss to follow-up at each assessment time point. After discussion with the YEF Assistant Director of Evaluation, the decision was taken to use the upper end of this sample size calculation range (N=288). Any harmful effects will be monitored through serious incident reporting. The pre-test/post-test correlation also mirrors the results of the pilot trial (i.e., 0.523).

However, as subsequently requested by the YEF, this trial will use self-reported delinquency as the primary outcome. The rationale for this is:

- A core YEF strategic aim is to understand what works to reduce crime and violence, so YEF aims to select offending as the primary outcome in all YEF studies where it is plausible that the intervention will reduce it, e.g. it is included in the theory of change
- The primary outcome must be measured using a valid and reliable measure and there were no valid and reliable measures of other relevant outcomes that are highly connected to crime e.g. child criminal exploitation.
- The mitigations included since the pilot study to increase the chance of seeing impact on offending (e.g. screening YP, introducing anonymous reporting of outcomes by YP)
- The co-primary outcomes from the pilot study will be included as secondary outcomes so that it will still be possible to test for intervention effects on these.

Participants

Participants will be YP between 10-17 at risk of CLDN involvement or CCE being seen by child social care or related agencies in three London local authorities and their primary caregiver (PCG).

Inclusion criteria - YP and families

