imputation techniques but the precise techniques used will depend on the pattern and extent of missingness. We will comply with the YEF Guidance on Missing Data.

Compliance

We use FFT LLC's own guidance of defining and measuring family compliance with the intervention. This stipulates that the total dose will depend on the needs of the family. However, we will report on the number of families who attended at least one session, and consider how many families moved through how many phases of treatment, how many received a critical dose of 8 sessions, mean number of sessions received and how many were deemed to have completed treatment. We will also report on therapist fidelity to the FFT model. This data will be provided by FFT LLC using the clinical monitoring system completed by FPM therapists. We will also explore whether time from referral to first FFT session is associated with compliance and improvement in outcomes. If power permits, we will explore whether compliance and fidelity are associated with improvements in the primary outcome and in CCE and SDQ conduct problems.

As advised by the YEF Statistical Guidance we will use an Instrumental Variable approach. This will use a Two Stage Least Square Analysis guidance (2SLS) approach with group allocation as the instrumental variable for the compliance indicator. Results for the first stage will be reported alongside with i) the correlation between the instrument and the endogenous variable; and, ii) a F test.

Intra-cluster correlations (ICCs)

This is not applicable to the current trial.

Presentation of outcomes

Effect sizes will be calculated using Hedges' g. Hedges' g is specified using the following formula:

```
Hedges' g = (x1 - x2) / V((n1-1)*s12 + (n2-1)*s22) / (n1+n2-2) where:
```

x1, x2: The sample 1 mean and sample 2 mean, respectively

n1, n2: The sample 1 size and sample 2 size, respectively

s12, s22: The sample 1 variance and sample 2 variance, respectively

The confidence interval for the Hedge's g statistic is:

g±φ - 1 (1-(α /2))gse where:

 ϕ - 1 = the percent point function of the normal distribution

gse= the standard error of the g statistic

 $= \sqrt{(n1+n2)/n1n2 + g^2/2(n1+n2)}$

References

We will add in to revised version.

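### The SAP sets aside intra-cluster correlation, yet about ten clinicians deliver FFT-G to 144 families in one arm and no model term allows for it

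*SAP*

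**What the plan says.** The SAP's section on intra-cluster correlations is a single sentence: "This is not applicable to the current trial". No reason is given. Young people are randomised individually, 1:1, stratified by site.

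The SAP's Analysis section describes a linear mixed model whose random intercepts are at participant level. Its primary outcome section adds site as a fixed effect. Eq. 1 lists allocation, baseline offending, age, site and a term labelled study, but nothing for therapist or team. The standard error for Hedges' g, under Presentation of outcomes, also treats participants as independent.

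The staffing is in the protocol under Stakeholders and interests. For the 144 families: "To generate this capacity we considered 3 teams, each with 2 therapists and 1 supervisor". In addition, "we will include a floating/peripatetic FFT-G therapist who can work across all three Boroughs". Only the intervention arm receives FFT-G; the control arm receives varied existing local services.

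On sample size the SAP states: "Estimates used 80% power and p = 0.05 with an enrolment ratio of 1", and "Power calculations used one-sided tests because there is no recorded case of FFT having iatrogenic effects". Neither document mentions a therapist ICC or a design effect.

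**The concern.** Individual randomisation makes the arms comparable at entry. It does not make outcomes independent afterwards when many families in one arm share a therapist. This is a partially nested design: clustered by therapist in the FFT-G arm, and not clustered by that route in the SAU arm. A fixed site effect does not absorb the correlation, because therapists differ within a site.

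The documents give reason to expect such differences. The protocol's footnote to its fifth research question says that the FFT teams are entirely new. The SAP's Compliance section plans to report therapist fidelity and, if power permits, to relate it to outcomes. If therapists do differ, the confidence interval for the main effect is too narrow and the p-value too small. The stated power also takes no account of it.

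**Working it through.** **The plan's own figure.** "Based on the effect size for PCG-reported Family Functioning outcome in the pilot study (g = 0.36 (-0.32,1.03)), clincalc.com returned 238 participants". Per arm, n = 2(z_α + z_β)²/g².
- Two-sided 5%: 2(1.960 + 0.842)²/0.36² = 121.1, so 122 per arm and 244 in total, within 3% of 238.
- One-sided 5%: 2(1.645 + 0.842)²/0.36² = 95.4, so 96 per arm and 192 in total. The stated sidedness therefore does not reproduce 238, which is a separate matter.
- 238 × 1.1 × 1.1 = 288, which matches "increased to 288 to account for up to 10% loss to follow-up at each assessment time point".

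No version contains a clustering term.

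**Inputs.**
- Clinicians: 3 × (2 + 1) + 1 = 10.
- Completers: 288 × 0.9 × 0.9 = 233.
- Equal caseloads: 144/10 = 14.4 families each; × 0.81 = 11.7 analysed.
- Unequal caseloads: the protocol gives each team 14 cases per five months and the supervisor two families in the first year, which leaves about 6, 6 and 2. With 48 families per borough, the effective cluster size is Σm²/Σm = 48 × (36 + 36 + 4)/14² = 18.6; × 0.81 = 15.1. This leaves out the floating therapist. Giving that therapist a load of 6 yields 13.4, between the two.
- Therapist ICC: not in the documents; assumed 0.01 to 0.10.

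**Formulas.** In the FFT-G arm DE = 1 + (m − 1) × ICC; in the SAU arm DE is taken as 1. The variance of the difference is inflated by V = (1 + DE)/2, and the standard error by √V. The two-sided type I error is 2[1 − Φ(1.96/√V)] and the one-sided is 1 − Φ(1.645/√V). Unadjusted power is Φ(0.36√(233/4)/√V − z), where 0.36√(233/4) = 2.748.

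**At ICC 0.05.**
- m = 11.7: DE = 1.535, V = 1.268, √V = 1.126. Type I error 8.2% two-sided and 7.2% one-sided. Power Φ(2.440 − 1.96) = 68% and Φ(2.440 − 1.645) = 79%.
- m = 15.1: DE = 1.705, V = 1.353, √V = 1.163. Type I error 9.2% and 7.9%. Power Φ(2.363 − 1.96) = 66% and Φ(2.363 − 1.645) = 76%.

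**Over the range** (m = 11.7 to m = 15.1):

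| ICC | True SE / reported SE | Type I, two-sided | Type I, one-sided | Power, two-sided | Power, one-sided |
|---|---|---|---|---|---|
| 0 | 1.00 | 5.0% | 5.0% | 78% | 86% |
| 0.01 | 1.03 | 5.6%–5.8% | 5.5%–5.6% | 76% | 85%–84% |
| 0.05 | 1.13–1.16 | 8.2%–9.2% | 7.2%–7.9% | 68%–66% | 79%–76% |
| 0.10 | 1.24–1.31 | 11.4%–13.3% | 9.2%–10.4% | 60%–56% | 72%–68% |

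**Baseline adjustment.** The sample size table gives a pre/post correlation of 0.523. Adjustment removes individual variance but not therapist variance, so an ICC of 0.05 becomes 0.05/(1 − 0.523²) = 0.069. The two-sided type I error is then 9.4% to 10.8%. Power rises to 75%–79% two-sided or 84%–87% one-sided.

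A simulation of a baseline- and site-adjusted analysis without a therapist term (6:6:2 caseloads, 20,000 runs per setting) gave two-sided type I error of 5.1%, 5.9%, 10.8% and 16.5% at ICC 0, 0.01, 0.05 and 0.10. The fixed site effect did not remove the inflation.

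**The case against.** The strongest reply is that young people are individually randomised. If FFT-G changes nobody's outcome relative to SAU, it cannot matter which therapist a family had, and the test stays near its nominal level. Inflation requires a mean effect of zero with real variation between therapists, some doing better than SAU and some worse. It also requires inference to therapists other than these. Whether therapists are fixed or random is a choice of estimand. This stands, and it limits the claim. It does not justify leaving the choice unstated, because an efficacy result will naturally be read as applying to FFT-G rather than to ten individuals.

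Other limits also stand:
- No ICC is given, and at 0.01 the effect is trivial.
- Ten is not a ceiling on the number of clinicians. The protocol expects turnover and leave, and replacements would make clusters smaller.
- The supervisor caseload of two is stated for the first year only.
- On the plan's stated one-sided basis with baseline adjustment, power at ICC 0.05 still exceeds 80%.

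A reader might infer that SAU families share no provider. The documents do not support that. The protocol's list of expected SAU services includes parenting programmes, group work and mentoring, and every participant has an allocated caseworker. Control-arm clustering is possible but cannot be quantified from the documents.

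**Conclusion.** The point holds in conditional form and should be fixed. Clustering by therapist is applicable to this design, and the planned model ignores it. For any positive therapist ICC, the reported standard error is too small for inference beyond the therapists in the trial. With 12 to 15 analysed families per therapist and an assumed ICC of 0.01 to 0.10, the understatement is about 3% to 30%.

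A reader might infer that the type I error will certainly be too high, or that the trial is underpowered for its primary outcome. Neither follows. The first depends on an ICC that the documents do not give and on a null in which therapists differ around a zero mean effect. As to the second, g = 0.36 is the pilot effect on parent-reported family functioning, so none of these power figures is power for self-reported delinquency.

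**What to change.** - **Model.** Replace the one-line answer with a partially nested model: a therapist random effect in the FFT-G arm, site fixed, and Satterthwaite or Kenward-Roger degrees of freedom. Make it the main analysis or, at minimum, a pre-specified sensitivity analysis for the primary outcome. Report the therapist ICC.
- **Data.** Ask for therapist ID to be added to the clinical-monitoring extract. The items listed in the protocol and SAP Compliance sections do not include it.
- **Coding.** State in advance how families who never start FFT-G, or who change therapist, are assigned to clusters.
- **SAU arm.** Treat SAU participants as singletons and say that this is an assumption. If provider data exist, add a sensitivity analysis for shared SAU providers.
- **Power.** State that the calculation assumes no therapist clustering, and show power over ICC 0.01 to 0.10 on the sidedness that the plan uses.

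The cost is SAP wording, one data field and one variance component. Intervals will be somewhat wider, and an ICC from about ten therapists will be imprecise. Recruitment and delivery do not change. The protocol's timeline already schedules an SAP update for November 2025, which could carry the change.

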calculate effect sizes for primary and secondary outcomes. We will use structural equation modelling to test for mediators of treatment (which are listed as secondary outcomes above).

Based on evidence from the pilot trial it is possible that some outcome variables may be skewed, in particular the primary outcome. We will determine whether transformation or scaling is appropriate depending on the skew and distribution of the data.

The analytical approach has been determined a priori and will be conducted with R Studio and SPSS.

Primary outcome analysis

The primary outcome is the ISRD4 total score which is a continuous variable. All YP will complete this measure at baseline, 6 months after randomisation and 12 months after randomisation. The main test of treatment effect will be at 12 months after randomisation. The total score uses a sum of the total volume of delinquent acts using 14 questions. The response scale for each question can be from 0 to whatever the total number of acts reported is (although see above for transformation approach). A hierarchical linear mixed model will be used with site as a fixed effect.

Regression models will be adjusted by the baseline number of offences in the six months prior to randomisation and stratification factors; age group and site, as covariates. The regression model specification is detailed in eq. 1.

Eq. 1

OFF6i,j = α + β 1 (allocation)i,j + β 2 (OFF0)i,j + β 3 (age)i,j + β 4 (site)j + β 4 (study)j ϵ

Secondary outcome analysis

The secondary outcomes are:

- YP Child Criminal Exploitation measured by items added to the Self-Report Delinquency Scale (YP report).
- YP Substance Misuse measured by ISRD3 substance misuse subscale (YP report).
- YP Conduct Problems measured by the conduct problems subscale of the SDQ (YP and parent report).
- YP mental health and adjustment measured by total score and impact score on the SDQ (YP and parent report; impact score parent report only).
- Parental mental health measured by the DASS-21 (parent report).

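### The SAP's only defined effect size, Hedges' g, is computed from raw arm means, so it does not carry the adjustment of the primary model and can disagree with it

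*SAP*

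**What the plan says.** The SAP's Analysis section promises effect sizes for the primary and secondary outcomes, and its Presentation of outcomes section gives the only definition: "Effect sizes will be calculated using Hedges' g". The numerator is the difference between two sample means ("x1, x2: The sample 1 mean and sample 2 mean, respectively"). The denominator pools two sample variances ("s12, s22: The sample 1 variance and sample 2 variance, respectively"). The standard error ("gse= the standard error of the g statistic") is the usual two-independent-sample expression in n1, n2 and g, and the interval uses the normal quantile at 1 − α/2. The Protocol's Analysis section also promises effect sizes but gives no formula.

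The test of the treatment effect is a different calculation. Under Primary outcome analysis: "A hierarchical linear mixed model will be used with site as a fixed effect", and "Regression models will be adjusted by the baseline number of offences in the six months prior to randomisation". Eq. 1 has terms for allocation, baseline offending, age and site. Under Missing data, predictors of missingness found by logistic regression become covariates in the outcome analyses. Under Imbalance at baseline, the SAP relies on that same strategy rather than on formal tests.

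No sentence says that g is to be taken from the model.

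**The concern.** As written, the report would carry two estimates of the treatment effect that need not agree. One is the model coefficient, adjusted for baseline, age, site and any predictors of missingness. The other is a raw standardised difference that carries none of these. Chance imbalance in baseline offending passes into g but is largely removed from the model estimate. If baseline predicts outcome, the interval for g is also wider than the one the model supports. A reader could then meet a significant model result beside an interval for g that includes zero, and the SAP has no rule for which to believe. Because g is the only standardised effect the SAP defines, it is the figure most easily carried into comparisons with other trials.

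**Working it through.** Neither document states an interval width for this trial's g, so there is no figure of the plan's own to reproduce here. The check compares the SAP's standard error with the one that baseline adjustment would give.

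**Inputs**
- g = 0.36 and 238 analysed, so 119 per arm (SAP, Sample size calculations overview).
- r = 0.523, the only pre/post correlation stated (same section, from the pilot).
- The correlation for ISRD4 from baseline to 12 months is not given. The section says that "power calculations for this efficacy trial did not make use of SRD data from the pilot study". So r = 0.523 is an assumption, and a range of r is needed.

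**1. SAP formula**

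SE = √[(n1+n2)/(n1·n2) + g²/(2(n1+n2))] = √[238/119² + 0.36²/476] = √[0.016807 + 0.000272] = 0.131

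95% half-width = 1.96 × 0.131 = 0.256

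**2. Baseline-adjusted counterpart**

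The first term is multiplied by 1 − r² = 1 − 0.523² = 0.7265. The g² term, which reflects uncertainty in the SD, is left alone.

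SE = √[0.016807 × 0.7265 + 0.000272] = 0.112; half-width 0.219

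The ratio of widths is 1.170. Without the g² term it is 1/√(1 − r²) = 1.173. With all 288 analysed the half-widths are 0.233 and 0.199, and the ratio is the same.

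**3. Sensitivity to the unknown correlation**, 1/√(1 − r²) − 1:

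| assumed r | excess width of raw interval |
|---|---|
| 0.1 | 0.5% |
| 0.2 | 2% |
| 0.3 | 5% |
| 0.4 | 9% |
| 0.5 | 15% |
| 0.523 | 17% |
| 0.6 | 25% |
| 0.7 | 40% |

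**4. How often the two would give different verdicts**

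The simulation used normal data, 119 per arm, r = 0.523 and 8,000 trials per effect size. A baseline-adjusted ANCOVA stood in for the primary model, and both results were judged at two-sided 5%.

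| true g | only adjusted test significant | only raw g significant | total disagreement |
|---|---|---|---|
| 0.20 | 14.3% | 4.3% | 18.6% |
| 0.25 | 16.6% | 3.4% | 19.9% |
| 0.30 | 16.2% | 2.7% | 18.9% |
| 0.36 | 12.0% | 1.4% | 13.4% |

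Totals are taken from unrounded proportions.

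**5. Effect of a baseline imbalance**

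Under r = 0.523, an imbalance of 0.2 SD moves raw g by 0.523 × 0.2 = 0.10. With 144 per arm the SE of a standardised baseline difference is √(2/144) = 0.118. So 0.2 SD is about 1.7 SE, and an imbalance at least that large in either direction has a chance of roughly 9%.

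**The case against.** The strongest reply is that nothing here is invalid. In a randomised comparison with roughly normal data, the SAP's interval is a proper one for the unadjusted difference. The main test is the model, and its power is untouched by how g is presented. The imbalance shift in step 5 is chance variation that the raw interval already allows for, not bias. All of this stands, and it limits the point to precision and consistency of reporting.

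Several stronger readings are tempting, and the documents do not support them.

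- A reader might take 17% as the established excess for the primary outcome, or say that the interval amounts to discarding 27% of participants (r² = 0.523² = 0.27). Both rest on r = 0.523, which is not tied to ISRD4. The Protocol reports that the pilot's delinquency measure, a different scale, was heavily skewed with mostly zero responses, so the correlation could be quite different.
- A reader might call g the trial's headline result. The SAP does not rank it above the model estimate. It is simply the only effect size defined.
- A reader might infer that g is a complete-case estimate set against a model that uses partial data. The SAP does not say which data feed the sample means, and it leaves imputation open. Eq. 1 has a single outcome with baseline as a covariate, so taken literally it too would drop participants without that outcome.
- A reader might expect that, if the outcome is log-transformed, a rate ratio could be reported beside g. The SAP contemplates transforming the outcome within a linear model. With many zeros, a log transform needs an added constant, and the exponentiated coefficient is then not a rate ratio.

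**Conclusion.** The point holds as one of alignment between estimate and test. The SAP's g and its interval omit the baseline, age and site adjustment of the primary model and any missingness covariates. The cost in precision depends on a correlation that the documents do not give for ISRD4. It is negligible near r = 0.1, about 17% in interval width at the pilot's 0.523, and about 40% at 0.7. The 13–20% rate of conflicting verdicts rests on r = 0.523, normal data, two-sided 5% and ANCOVA as a stand-in for the model. The SAP itself expects skew in the primary outcome, so that rate is illustrative. Whatever r turns out to be, the mismatch in what is being estimated remains, and removing it costs nothing.

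**What to change.** In Presentation of outcomes, replace the definition, for primary and secondary outcomes alike, with:

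- g = adjusted arm difference at 12 months from the primary model ÷ pooled unadjusted SD at 12 months.
- 95% CI for g = the model-based 95% limits for that difference ÷ the same SD.
- If an outcome is transformed, compute the difference and the SD on the scale used in the model, and state that scale.

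Dividing the limits by the SD treats it as known. At the planning values this matters little (ratio 1.173 against 1.170 in the working). Raw arm means and SDs can be reported descriptively beside g.

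The cost is a rewrite of one SAP section. It needs no new data or extra participants and leaves the primary test unchanged. It should be made before outcome data are linked to allocation.
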